10.2 Secondary Aims - Efficacy

Primary outcomes for secondary aims

Changes in myocardial performance index as measured by pulse wave Doppler echocardiography over 12 months of the follow-up from the extension trial baseline till end-of-study testing will be calculated. Student's t-test for location will be used to determine if mean change is different from zero. A similar approach will be applied to maximal oxygen consumption determined by exercise testing for subjects who reached maximal effort at both time points.

Similarly, changes in serum BNP level and pulse amplitude tonometry ratio derived from the EndoPAT device over 12 months of the follow-up from the extension trial baseline till end-of-study testing will be calculated. The Wilcoxon signed rank test for location will be used to determine if median change of each of these outcomes is different from zero.

For secondary efficacy aim focused on maximal oxygen consumption, estimated power to test potential secondary hypothesis is calculated conditional on the target sample size of 250 subjects (a conservative estimate for number of subjects with paired max effort exercise measurements). The estimate below is provided strictly as an illustration, since there will be no formal hypotheses testing for secondary outcomes.

Assuming 250 subjects with paired max effort exercise measurements, baseline mean value of maximal VO₂: 28.0±6.25 ml/kg/min and correlation between baseline and 12-month measurements for maximal VO₂: 1/3 (based on historical data; a conservative assumption),

we'll have 85% power to detect change of 1.4 ml/kg/min (or 0.2 of standard deviation) with type 1 error of 0.05.

Secondary outcomes for secondary aims

Secondary outcomes include submaximal measures of exercise capacity (based on exercise testing), measures of systolic and diastolic function (based on echocardiograms), and results of quality of life surveys measured at baseline and 12-month follow-up visit. Descriptive statistics will be provided for each outcome at both time points. Mean change values of the outcomes will be assessed by a paired t-test.

Missing data

Since the main goal of the follow-up study is to assess safety of the patients, imputation of missing data is not planned.

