6.3.2 Measures of Secondary Aims (Pharmacodynamics)

Primary Outcomes:

- Exercise: Change in maximal oxygen consumption from FUEL extension baseline (will be end-of-study testing for FUEL participants) to testing at 12 months measured using a standardized exercise test.
- Echo: Change in myocardial performance index as measured by pulse wave Doppler echocardiography from baseline to testing at 12 months.
- Endothelial Function: Change in log-transformed Reactive Hyperemia Index derived from the EndoPAT® device.
- Functional Health Status: Change in full scale Peds QL
- Biomarkers: Change in serum BNP level from baseline to testing at 12 months.

Secondary Outcomes:

- Exercise: Submaximal measures of exercise capacity will be collected and evaluated.
- Echo: Measure of systolic and diastolic function will be collected from a targeted echocardiogram.
- Functional Health Status: Change in Peds QL physical functioning score, psychosocial functioning score, and cardiac-specific quality of life score. Change in Pediatric Cardiac Quality of Life Inventory (PCQLI) score.
- Arrhythmia Burden (limited to non-FUEL subjects; participation is optional) will be assessed at 2 time points: pre-study drug and post-study drug (both during the baseline visit): Number of premature atrial or ventricular beats (2 outcomes) as a percentage of total beats over the course of heart-rhythm monitoring from pre-study drug measurements compared to taking study drug. Occurrence, duration and speed of atrial or ventricular

arrhythmias (2 outcomes), and comparison between the two time points.

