6.4 Study Visits

Baseline Visit – For those subjects who WERE participants in the FUEL Trial:

1. Baseline screen

Prior to study enrollment, patients will be screened to ensure that all inclusion criteria are met and none of the exclusion criteria are present. The safety labs for FUEL will be accepted as meeting the inclusion criteria for FUEL extension. Pregnancy testing for OLE will be done at every in-person visit via a urine or serum pregnancy test for female participants. If the pregnancy test is positive all further testing will be stopped, the patient will not be enrolled into the trial and the result will be conveyed to the subject and/or guardians by the site-principal investigator in accordance with local IRB procedures.

2. Informed consent

Informed consent and assent for FUEL Extension will be obtained (if not obtained prior) as per local IRB/REB requirements during the end-of-study visit for FUEL.

3. Baseline PD testing

End-of-study pharmacodynamic testing for FUEL will serve as baseline testing for FUEL Extension.

4. Quality of life surveys

End-of study quality of life survey results (Peds QL, Peds QL cardiac specific module, PCQLI), HAES for FUEL will serve as baseline testing for FUEL Extension

5. Initiation of study drug (See Table 2)

Subjects will return to their study center in the shortest period of time deemed practical, following FUEL study completion, for study drug initiation under direct observation. During this visit, a resting blood pressure and heart rate will be obtained just prior to dosing. One dose of the study medication will be administered to the subject. At approximately 2 hours (+/- 30 minutes) post dosing, an additional resting heart rate and blood pressure will be measured and the subject will be asked to perform a self-limited 6-minute walk. A repeat heart rate and blood pressure will be measured immediately following the 6 minute walk and a blood sample will be obtained for determination of udenafil and metabolite concentration. At approximately 2 hours (+/- 30 minutes) following the 6-minute walk, a final resting heart rate and blood pressure will be obtained, adverse events will be recorded, and the subject will be dispensed their initial supply of study medication. The subject will be instructed to take the medication twice a day and to bring back the medication bottle for their next in-person visit.

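### Section 10.2 tests one pooled 12-month change per outcome, but the extension baseline follows FUEL udenafil for some subjects and precedes study udenafil for others; report change by prior exposure

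*Combined protocol and SAP*

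**What the plan says.** Section 10.2 computes each change from extension baseline to 12 months.

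- For myocardial performance index a Student "t-test for location will be used to determine if mean change is different from zero", and maximal VO2 is handled in the same way.
- For BNP and the tonometry ratio a Wilcoxon "signed rank test for location will be used to determine if median change of each of these outcomes is different from zero".
- For the secondary outcomes, including quality of life: "Mean change values of the outcomes will be assessed by a paired t-test".

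No stratum, covariate or subgroup for earlier FUEL treatment appears in that section.

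The baseline for rollover subjects is set in section 6.4: "End-of-study pharmacodynamic testing for FUEL will serve as baseline testing for FUEL Extension". The same holds for the surveys: "End-of study quality of life survey results (Peds QL, Peds QL cardiac specific module, PCQLI), HAES for FUEL will serve as baseline". Section 6.3.2 repeats that the maximal VO2 baseline "will be end-of-study testing for FUEL participants". FUEL treatment lasts six months (synopsis, Significance). Section 10.4 names the sources of subjects: the FUEL udenafil arm, the FUEL placebo arm, and people who were not in FUEL.

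The plan states two questions for these data. Secondary Aims 1 and 2 in section 4.2 hypothesise improvement after udenafil is given. Sections 5.3 and 5.4 ask whether any FUEL improvement lasts.

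Section 10.2 also gives a power figure for maximal VO2 and says that it "is provided strictly as an illustration, since there will be no formal hypotheses testing for secondary outcomes".

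**The concern.** The word baseline means two things here. For former udenafil-arm subjects it is an on-treatment value after six months of assigned drug. For everyone else it is a value before any study udenafil. One mean change over both groups averages a change after starting with a later change in people already exposed.

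The first quantity bears on the improvement hypothesis, the second on durability. The pooled number isolates neither, and it moves with the proportion of each group enrolled even if the drug acts identically. If benefit comes early and is then held, prior users pull the pooled change towards zero. If prior users lose ground while starters gain, the pooled value hides it. A reader of the pooled result could not tell these cases apart.

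No other section repairs this. The clinical factors in section 6.3.3 are examples, and prior FUEL arm is not among them. The by-arm comparison in section 10.4 covers FUEL subjects who do not join the extension. Its expectation of no rollover/new difference rests on identical entry criteria, which do not equalise prior exposure.

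**Working it through.** **Inputs from section 10.2.** The plan's wording is "Assuming 250 subjects with paired max effort exercise measurements"; SD 6.25 ml/kg/min; correlation 1/3; change 1.4 ml/kg/min; type 1 error 0.05 (sidedness not stated, two-sided taken); stated power 85%.

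**Assumed, not in the documents.** Equal SD at both visits; the share f of the 250 pairs with prior udenafil; the true change in each group. FUEL's allocation ratio and the final enrolment mix are not given.

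**Step 1: the plan's own figure.** SD of change = 6.25 × √(2 × (1 − 1/3)) = 7.217. Standard error = 7.217/√250 = 0.456. Noncentrality = 1.4/0.456 = 3.07. Two-sided one-sample t power = 86.3%. The stated 85% is reproduced.

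**Step 2: what the pooled mean estimates.** With starters (no prior study udenafil) changing by a and prior users by b, the pooled mean is (1 − f)a + fb.

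- *It depends on the mix.* With a = 1.4 and b = 0, it is 1.05, 0.93 and 0.70 at f = 1/4, 1/3 and 1/2.
- *It does not identify the pattern.* At f = 1/2: 0.5 × 1.4 + 0.5 × 0 = 0.70; 0.5 × 0.7 + 0.5 × 0.7 = 0.70; 0.5 × 2.1 + 0.5 × (−0.7) = 0.70. These are, respectively, a gain on starting with no further change in prior users, equal gains, and a gain on starting with a loss in prior users.

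**Step 3: does pooling cost power?** Pooled variance = 7.217² + f(1 − f)(a − b)², with n = 250 and a = 1.4. The last column takes starters alone at 1.4.

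| f | Pooled, b = 0 | Pooled, b = 0.7 | Pooled, b = 1.4 | Starters alone (n) |
|---|---|---|---|---|
| 1/4 | 63% | 76% | 86% | 75% (188) |
| 1/3 | 53% | 72% | 86% | 70% (167) |
| 1/2 | 33% | 63% | 86% | 58% (125) |

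With b = 0 the pooled test is weaker than starters alone. With b = 0.7 or 1.4 it is stronger. The direction turns on b, which is unknown.

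**Step 4: precision after a split.** The 95% CI half-width is t(0.975, n − 1) × 7.217/√n.

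| Group | n | Half-width, ml/kg/min |
|---|---|---|
| Pooled | 250 | 0.90 |
| No prior udenafil, f = 1/4, 1/3, 1/2 | 188, 167, 125 | 1.04, 1.10, 1.28 |
| Former udenafil arm, f = 1/4, 1/3, 1/2 | 62, 83, 125 | 1.83, 1.58, 1.28 |

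**The case against.** The strongest reply is that these are secondary outcomes in a safety study, that section 10.2 itself disclaims formal testing, and that the open-ended list in section 6.3.3 already permits an analysis by prior arm. All of that stands, and it limits the weight of the point. It does not remove it: a descriptive estimate still has to mean something definite, section 10.2 specifies the tests anyway, and permission is not commitment.

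A reader might infer more than the documents support in four ways.

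- *That pooling loses power.* The loss in step 3 appears only if prior users do not change further. If they gain half as much as starters, pooling does better than starters alone. The range of f shown is also an assumption, and section 10.4 allows that one FUEL arm may be over-represented.
- *That the end-of-FUEL baseline is a mistake.* It is a deliberate choice (section 5.4) and suits the durability question in the former udenafil arm.
- *That durability cannot be assessed without pre-FUEL values.* FUEL measures its own gain. End-of-FUEL to Week 52 in the former udenafil arm shows at group level whether that level was held. The pre-FUEL value adds context only.
- *That former udenafil subjects were treated without a break.* Section 6.4 has them return for observed initiation as soon as practical after FUEL, with no maximum interval. Uninterrupted treatment is not established.

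Section 10.4's expectation of no difference concerns entry criteria and makes no claim about response, so editing it is optional.

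**Conclusion.** The point holds as one of interpretation. Section 10.2 plans one estimate over groups whose baselines differ in prior exposure, and that estimate answers neither of the plan's stated questions separately. This follows from the text and needs no numerical assumption. The size does need one: under assumed exposed shares of one-quarter to one-half, the same group effects (+1.4 and 0) give pooled changes from 1.05 down to 0.70 ml/kg/min, and a single pooled value fits opposite patterns in prior users.

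No general power loss is shown, and the plan's 85% is right for its own inputs. The primary aim, adverse events, is untouched. This is a cheap improvement to non-confirmatory secondary reporting.

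**What to change.** In section 10.2:

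- Report each pharmacodynamic and quality-of-life change with a 95% CI for former FUEL udenafil, former FUEL placebo and new subjects, and for the last two combined as no prior study udenafil.
- Base the statement about improvement on the combined group.
- Base the statement about maintenance on the former udenafil arm, from end-of-FUEL to Week 52, with the pre-FUEL value shown descriptively.
- Keep the pooled change as descriptive.

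Add prior FUEL arm to the list in section 6.3.3.

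State the limits alongside:

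- All are uncontrolled before-after estimates, subject to the decline in exercise performance described in section 5.1. This applies to any pre-FUEL comparison as well.
- The interval between end-of-FUEL testing and restarting drug is not fixed.
- The intervals are not adjusted for multiplicity.
- The split is post hoc if added after Week 52 data were seen. Section 6.4 of the current version already provides for participants who have finished the 24-month extension, so some Week 52 data exist; the documents do not say whether anyone had examined them.

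The cost is SAP wording, extra table columns and linkage to rollovers' FUEL baseline records. No visits or subjects are added. The real price is precision: half-widths of about 1.0 to 1.8 ml/kg/min against 0.90 pooled at the assumed shares, and wider still for placebo and new subjects shown separately. At 62 or 83 former udenafil pairs the half-width exceeds 1.4, so the maintenance estimate would be imprecise.

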10.3 Interim analyses

No formal stopping rules for safety or efficacy are planned. However, the trial data will be reviewed on a periodic basis, at least twice per year, by the DSMB. The DSMB report will include information on safety, data quality and data completeness, overall and by center. The DSMB has the jurisdiction to recommend stopping of the trial early due to safety concerns at any time. The DSMB can recommend stopping the trial after reviewing the results of the FUEL trial if the results of FUEL suggest that continuing with FUEL extension is not necessary.

10.4 Potential Biases

Enrollment to the open label extension trial (OLE) will have two sources: rollover subjects who were previously enrolled in one of the FUEL arms (udenafil, placebo) and new subjects who didn't participate in FUEL. Since inclusion/exclusion criteria are identical for the FUEL and OLE, we don't expect differences between the rollover and new subjects.

OLE subjects will not include FUEL subjects who dropped-out or didn't consent to OLE, creating the theoretical potential for one arm of FUEL (placebo or study drug) to be over-represented in OLE. Incidence of AEs and key patient characteristics of FUEL subjects not participating in OLE will be compared by treatment arm to assess potential bias.

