7. SELECTION AND WITHDRAWAL OF SUBJECTS

7.1 Subject Inclusion Criteria

1. Males and females with Fontan physiology who participated in the FUEL trial or, if they did not participate in FUEL, those who are 12 to less than 19 years of age at enrollment.
2. Participant consent or parental/guardian consent and participant assent
3. Participant fluent in English or Spanish
4. Current anti-platelet or anticoagulant therapy

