7.2 Subject Exclusion Criteria

1. Height < 132 cm.
2. Weight < 40 kg.
3. Hospitalization for acute decompensated heart failure within the last 12 months.
4. Current intravenous inotropic drugs.
5. Undergoing evaluation for heart transplantation or listed for transplantation.
6. Diagnosis of active protein losing enteropathy or plastic bronchitis within the last three years, or a history of liver cirrhosis.
7. Known Fontan baffle obstruction, branch pulmonary artery stenosis, or pulmonary vein stenosis resulting in a mean gradient of > 4 mm Hg between the regions proximal and distal to the obstruction as measured by either catheterization or echocardiography.
8. Single lung physiology.
9. Maximal VO₂ less than 50% of predicted for age and gender at enrollment.
10. Severe ventricular dysfunction assessed qualitatively by clinical echocardiography within six months prior to enrollment.
11. Severe valvar regurgitation, ventricular outflow obstruction, or aortic arch obstruction assessed by clinical echocardiography within six months prior to enrollment.
12. Significant renal, hepatic, gastrointestinal or biliary disorders that could impair absorption, metabolism or excretion of orally administered medications.
13. Inability to complete exercise testing at baseline screening.
14. History of PDE-5 inhibitor use (with the exception of FUEL participation) within 3 months before study onset.
15. Use of any other drug to treat pulmonary hypertension within 3 months before study onset.
16. Known intolerance, including hypersensitivity or allergy history, to oral udenafil or any components of the investigational product.
17. Frequent use of medications or other substances that inhibit or induce CYP3A4.
18. Current use of alpha-blockers or nitrates.
19. Ongoing or planned participation in another research protocol that would either prevent

successful completion of planned study testing or invalidate its results.

- 20. Noncardiac medical, psychiatric, and/or social disorder that would prevent successful completion of planned study testing or would invalidate its results.
- 21. Cardiac care, ongoing or planned, at a non-study center that would impede study completion.
- 22. For females: Pregnancy at the time of screening, pregnancy planned before study completion, or refusal to use an acceptable method of contraception for study duration.
- 23. Unable to abstain or limit intake of grapefruit juice during the duration of the trial.

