10. STATISTICS

10.1 Primary Aim - Safety

The primary safety outcome is adverse events. The adverse events will be reported by seriousness, severity and relationship with the study drug. Additionally, the number of subjects experiencing a composite outcome of death, heart failure associated hospitalization, or heart transplant will be reported. The overall assessment of safety will be made on the basis of all available adverse events and safety outcome data over the duration of the 12 months extension trial and an additional 90 days following completion of the study protocol.

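### Identical criteria do not make previously treated and first-time udenafil users comparable, so the pooled adverse-event incidence can understate tolerability risk in first-time users

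*Combined protocol and SAP*

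**What the plan says.** Section 10.4 starts from the premise "Since inclusion/exclusion criteria are identical for the FUEL and OLE" and concludes that rollover and new subjects are not expected to differ. The same paragraph names the sources of enrolment: "rollover subjects who were previously enrolled in one of the FUEL arms (udenafil, placebo) and new subjects who didn't participate in FUEL". That makes three exposure histories: former udenafil, former placebo and new.

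The next paragraph of 10.4 recognises selective entry: "OLE subjects will not include FUEL subjects who dropped-out or didn't consent to OLE". It treats the risk as one FUEL arm being over-represented and plans a check: "Incidence of AEs and key patient characteristics of FUEL subjects not participating in OLE will be compared by treatment arm to assess potential bias".

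Exclusion 16 in section 7.2 removes anyone with "Known intolerance, including hypersensitivity or allergy history, to oral udenafil or any components of the investigational product". Inclusion 1 in section 7.1 admits those "who participated in the FUEL trial or, if they did not participate in FUEL, those who are 12 to less than 19 years of age".

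For the primary outcome, section 10.1 says: "The adverse events will be reported by seriousness, severity and relationship with the study drug". The safety conclusion rests on all events together. No breakdown by prior FUEL arm or by recruitment source is planned. Section 6.3.3 gives examples of covariates to explore against safety outcomes, and neither factor is among them.

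**The concern.** Two groups can meet the same written criteria and still differ in the feature that matters for a tolerability estimate, namely whether they have already taken the drug and stayed on it. A person who has never taken udenafil can hardly have a known intolerance to it. Exclusion 16 therefore acts mainly on the former udenafil arm, and drop-out and non-consent can act in the same direction.

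The extension has no comparator, and the hypothesis in section 4.1 is that udenafil is safe and tolerable over 12 months. The plan itself treats starting the drug as a point of risk: the first dose is observed, and calls follow the next day and then weekly for four weeks (sections 6.4 and 9.1). For former udenafil-arm subjects that period is re-exposure. Pooling them with first-time users can dilute the early reactions and intolerance discontinuations that this monitoring is meant to catch.

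**Working it through.** The documents give no adverse-event rate for the extension, no intolerance rate, no FUEL allocation ratio and no rollover mix. There is thus no planned figure to reproduce, and what follows shows a range under stated assumptions.

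**Inputs from the documents.** About 400 potential rollovers and a minimum enrolment of 300, with new subjects added only if rollovers fall short (sections 6.1 and 7.3). FUEL treatment lasted about six months (synopsis, Significance).

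**Assumptions.** FUEL was randomised 1:1, and uptake of the extension is otherwise equal by arm. A share f of 2% to 10% is intolerant. Every intolerant person has the event on first exposure and none enters from the former udenafil arm. Tolerant subjects have risk p in every group.

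**Formulas.** With R rollovers before removal of the intolerant and N new subjects:

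- former-udenafil share u = (R/2)(1−f) / [(R/2)(1−f) + R/2 + N]
- risk in first-time users P = f + (1−f)p
- pooled risk = u·p + (1−u)·P
- understatement = u·f·(1−p)

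With N = 0, R cancels and u = (1−f)/(2−f), so 300 and 400 rollovers give the same answer.

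**Worked case.** Take all rollovers and f = 5%, so u = 0.95/1.95 = 0.487.

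- Event that defines intolerance (p = 0): P = 5.0%, pooled = 0.513 × 5.0% = 2.6%, difference 2.4 points.
- Common event (p = 0.33): P = 0.05 + 0.95 × 0.33 = 36.3%, difference = 0.487 × 0.05 × 0.67 = 1.6 points.

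| Cohort | f | u | p = 0: first-time vs pooled (difference) | p = 0.33: difference | p = 0.67: difference |
|---|---|---|---|---|---|
| All rollover | 2% | 0.495 | 2.0% vs 1.0% (0.99) | 0.66 | 0.33 |
| All rollover | 5% | 0.487 | 5.0% vs 2.6% (2.44) | 1.63 | 0.80 |
| All rollover | 10% | 0.474 | 10.0% vs 5.3% (4.74) | 3.17 | 1.56 |
| 200 rollover + 100 new | 2% | 0.329 | 2.0% vs 1.3% (0.66) | 0.44 | 0.22 |
| 200 rollover + 100 new | 5% | 0.322 | 5.0% vs 3.4% (1.61) | 1.08 | 0.53 |
| 200 rollover + 100 new | 10% | 0.310 | 10.0% vs 6.9% (3.10) | 2.08 | 1.02 |
| No rollovers | any | 0 | equal (0) | 0 | 0 |

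Differences are in percentage points. For scale only, Table 3 in section 13.1 shows 2 of 6 subjects with flushing and 4 of 6 with headache at the study dose.

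For intolerance-defining events the relative understatement equals u: 47% to 50% with all rollovers and 31% to 33% with 200 plus 100. With all rollovers it is 1.9% to 8.0% at p = 0.33 and 0.5% to 2.2% at p = 0.67.

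**Does the planned check cure this?** It describes FUEL subjects who did not enter, by arm. It could show excess adverse events among udenafil-arm non-entrants, but it neither separates nor adjusts the rates among those who did enter.

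**The case against.** Several points on the other side have weight.

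- **Selective entry is recognised.** Section 10.4 names drop-out and non-consent and plans a by-arm look at non-entrants. That is a useful warning signal, but it leaves the reported extension incidence pooled.
- **FUEL covers early reactions.** FUEL has a placebo arm and evaluates six-month safety, and the extension is meant to supplement it with longer-term data. Risk in first-time users is not an estimand the protocol names. This limits the importance of the point. It does not make the 10.4 inference valid.
- **The mechanism is not clean.** Former placebo subjects also stayed in FUEL and consented. If assignment was still masked at rollover, which is not stated, some with presumed reactions could have been screened out too. Former udenafil subjects carry about six more months of exposure, which could raise late or cumulative events. The direction is argued only for tolerability-type events.

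A reader might infer more than the documents support:

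- **That the criteria are shown not to be identical**, because the age limit binds only new subjects and exclusion 14 exempts FUEL use. FUEL's own criteria are not in the documents, so this cannot be shown. The age clause may simply let FUEL subjects who have grown older continue, and the exemption is needed for any rollover. The argument does not depend on it.
- **That the sildenafil pilot crossover table in section 13.1 gives the size** (headache 33% on drug, 18% on placebo). Putting tolerance-selected subjects at the placebo rate would require f = (0.33 − 0.18)/(1 − 0.18), or about 18% of the udenafil arm removed. Headache is a listed expected event (section 9.2.2), and having one is not in itself known intolerance. The data come from another drug over six weeks.
- **That the composite of death, transplant and heart-failure admission is biased.** Nothing in the documents links it to selection for tolerance.

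**Conclusion.** The inference in 10.4 does not follow, and 10.1 has no analysis that would reveal the problem. The pooled 12-month incidence of tolerability-type events can understate the risk in first-time users; the documents do not establish that it will, or by how much. Under the assumptions shown, the understatement of intolerance-defining events runs from nil to about half (up to 4.7 points). For common events it is at most 3.2 points. These ranges rest on the assumed 1:1 allocation, equal uptake, 2% to 10% intolerance and complete removal of intolerant subjects from the former udenafil arm. Incomplete removal would make the effect smaller. The point is worth acting on because the remedy is cheap and replaces an invalid argument with data.

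**What to change.** In section 10.4, delete the conclusion that no differences are expected. State instead that former udenafil-arm entrants may be selected for tolerance.

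In section 10.1, report adverse events and discontinuations for intolerance by prior exposure (former FUEL udenafil, former FUEL placebo, new) beside the pooled total, once FUEL assignment is available. If new subjects are few, combine them with former placebo subjects as a first-exposure group. Also report how many FUEL udenafil-arm subjects did not enter because of intolerance. The composite does not need splitting on this ground.

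The change uses recruitment source, which the extension records, and FUEL assignment, which the by-arm comparison in 10.4 already requires. It needs no new data. The cost is extra table columns and wider intervals in the smaller groups, so the split should be presented as descriptive.
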